Men, in general, are harder to engage in traditional disease prevention programs using traditional diet and PA interventions (19). Several studies have translated the DPP to be culturally-specific to the Hispanic community in various settings but predominantly in females.(20, 21) **Hispanic men are significantly understudied** and we are not aware of DPP translational programs tailored to Hispanic male populations. These community-based approaches had retention rates ranging between 63-93% after the core sessions at 6 months. These approaches worked well in females, but there was **little discussion on what drove the lack of recruitment in males.** Furthermore, previous DPP translation trials typically lack reporting of PA results, one of the pillars of the program, specifically objectively-measured PA.(22)

Using technology in an intervention setting can be a simple, efficient, motivational substitute to the traditional DPP format. An abbreviated mobile application version of the DPP was employed effectively in a multiethnic population in San Francisco. This study provided an iOS mobile app in combination with an in-person five month DPP. (23) This group of mostly middle-aged (mean 55 years) females had a retention rate of 93% at five months with a mean 7% weight loss. (23) A 13-week diabetes prevention program was implemented in Northern Mexico, in which 63% of the 184 participants completed the intervention. This mostly female cohort improved their fasting glucose by 7.5 ng/dL after a 3-month follow up. (24) In summary, the DPP can be adapted to a Hispanic community and abbreviated to coincide with a RS intervention.

Our objective is to harness the popularity of RS in local Atlanta Hispanic males and determine the feasibility of a RS implementation in combination with online education and facilitated lifestyle coaching to decrease T2DM

risk. Translating the DPP with a simple online tool and alongside a free opportunity to play a venerated sport in a supportive atmosphere may prove to be exactly what is needed for adherence in Hispanic males.

Protocol Synopsis

Study Design: A longitudinal pre-post pilot intervention study evaluating feasibility of implementation of a soccer-based Diabetes Prevention Program and preliminary changes in physical activity and diet-related measures.

Planned Sample Size: 40 subjects

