Subject population: Hispanic overweight males age 35 to 55 years with a CDC pre-diabetes risk score ≥ 9 and not currently engaged in soccer or other regular physical activity.

Specific Aims

We will test the following central hypothesis: **A soccer-based adaptation to the DPP can be feasibly implemented in a population of middle-age Latino men at high risk for T2DM.**

Aim 1: *1a:* To adapt the current National Diabetes Prevention Program (NDPP) curriculum to a novel, translational soccer-based DPP programming and delivered by trained coaches as facilitators.

1b: To conduct formative research addressing barriers and acceptability for implementation of this soccer-based DPP adaptation among Latino adults via questionnaires and key informant interviews.

Aim 2: *2a:* To assess implementation feasibility of this novel soccer-based DPP adaptation by conducting a single-arm, pre-post pilot study among Latino males (n=40; 35-55 years) residing in the Atlanta metro area.

2b: To explore preliminary signals for improvements in objectively-measured PA, dietary behaviors, physical fitness and body composition outcomes with our soccer-based DPP adaptation.

Overweight (BMI between 25 and 60 kg/m²) participants at high risk for T2DM (CDC pre-diabetes screening tool score >9)(25) will be recruited through soccer interest groups, local leagues and Hispanic health organizations. After a baseline assessment visit, participants will attend soccer practice twice/week for 12-weeks while completing NDPP core curriculum modules with facilitated discussion by trained coaches during each soccer practice. Participants will then be invited to join an established small-sided soccer league in their community (12-weeks) offering one game/week and also complete the NDPP maintenance modules and PA/diet self-tracking via mobile health technologies. After the core (12-weeks) and maintenance intervention periods (24- weeks) baseline measurements will be repeated. We will also conduct a 1-year follow up assessment after 6 months of minimal contact. Data on the feasibility of this DPP soccer-based adaptation will inform future randomized, controlled trials testing the effectiveness of this translation model to reduce T2DM risk while extrapolating to other sports-based adaptation and age, gender and racial sub-populations.

Research Design:

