- 3) CDC pre-diabetes risk score ≥ 9 (25)
- 4) Not currently engaged in soccer practice or league or other PA or lifestyle intervention program
- 5) Ability to read in English or Spanish and provide informed consent

Exclusion criteria

- 1) T2DM diagnosis or medication
- 2) BMI ≥ 41
- 3) Resting blood pressure $\geq 165/100$ at screening
- 4) Any mobility issues or contraindications for HIIT PA program (26)

Recruitment: Participants will be recruited from the mentioned local Atlanta area organizations using online a study recruitment flier in both print and electronic format. Interested participants will be provided an online survey to ascertain eligibility (CDC pre-diabetes screening, demographic questions and PA habits) and those meeting inclusion criteria will be invited to an informative session at one of participating soccer field for informed consent and confirmatory baseline assessments including BMI, blood pressure, HbA1c and exercise pre-participation risk screening. Siemens DCA Vantage HbA1c point-of-care devices will be used for screening of diabetes. (27) A cut off point of 6.5% will be used as a putative definition of diabetes and these individuals will be referred to a local clinic for confirmatory testing and appropriate management. (28) Both systolic and diastolic blood pressure will be measured while sitting using a calibrated electronic blood pressure sphygmomanometer prior to any activity and after five minutes of rest. Participants meeting inclusion and exclusion criteria will be invited to participate in the study.

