Study Assessments. Prior to testing, subjects will be asked to refrain from physical activity for 48 hours prior to test day, refrain from alcohol 24 hour prior to testing, and refrain from caffeinated drinks, smoking and other stimulants one hour prior to testing. Assessments will be conducted at baseline during the first soccer practice and after the 12-week initial soccer conditioning phase. Assessments will also be repeated at 24-weeks and 1 year from study initiation at the final monthly meeting after the soccer league (maintenance phase of the program) has been completed. Blood pressure, HbA1c, height and weight, waist circumference, aerobic and musculoskeletal fitness assessments will be performed. In addition, questionnaires will be used for self-reported physical and mental health, quality of life, PA and diet self-efficacy, program satisfaction and injuries. Dietary recalls will be conducted at baseline, 12, 24 weeks, and 1 year and by trained staff and analyzed using Nutrition Database System for Research.(29) Participants will participate in online education modules located on the CDC website during an initial 12 week conditioning phase where they will participate in soccer drills and other fitness routines (two 1-hour sessions per week). At the 12 week mark participants will transition onto a soccer league team for the following 12 weeks where they will continue to complete online modules and meet with the soccer coach monthly to discuss. There will be a 1-year follow up to be conducted 6 months from the final soccer session to complete all measurements again. During the soccer sessions/games participants will

be fitted with a wearable soccer-specific device to measure how much they move and their heart rate. All of these measurements will be done on the soccer field. In addition, they will also be asked to wear a Garmin fitness tracker for the duration of the study to measure steps and moderate and vigorous activity. The online education will be a version of the Diabetes Prevention Program and can be completed on a phone or computer with internet access. We will send reminders by text message to do the online education and the soccer coach will talk to the soccer team during soccer practice about what they've learned and answer any questions they may have about the education material.

Informed Consent Process:

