Human Subjects Involvement and Characteristics. We will recruit 40 subjects for this study who are overweight or obesity class 1. Subjects will be required to meet the following inclusion criteria: 1) Hispanic/Latino men aged 35-55 years; 2) BMI $\geq 27 \text{ kg/m}^2$; 3) CDC pre-diabetes risk score ≥ 9 ; 4) not currently engaged in soccer practice or other PA or lifestyle intervention program; 5) ability to read in English or Spanish and provide informed consent; Exclusion criteria are participants with 1) T2DM diagnosis or medication; 2) BMI ≥ 33 ; 3) resting blood pressure $\geq 165/100$ at screening 4) any mobility issues or contraindications for HIIT PA program. Subjects will be recruited from local Atlanta area Latino health centers. Each subject will receive a free intervention performed by trained soccer coaches in a small group format. Enrollment fees for league play will be covered by the study. Retention of these subjects will be aided by text messages given through the app technology used to track physical activity. **Research Material Collected:** These will include medical history (previous diagnoses), demographic information, anthropometrics, blood pressure, HbA1c, physical activity assessments and tracking of physical activity via a fitness tracker throughout the study.

Potential Risks:

There is some mild discomfort with the finger stick required by the HbA1c point-of-care device. Standard sterile techniques will be used; thus, infection is unlikely. There is small-to-moderate risk of injury with the most common being muscle strains and joint sprains while playing soccer and during conditioning. However, we will implement an evidence-based approach proven to reduce in up to 40% the risk of common soccer injuries and protocols to screen for exercise-related adverse events. Soccer coaches will be certified in cardio-pulmonary resuscitation and soccer field protocols for emergency situations reviewed and improved as needed, including availability of AED's. There is a small risk of loss of confidentiality. We will follow all procedures required by Emory University to protect participants. Efforts will be made to ensure that all personal information remains confidential. All data will be stored in locked offices and password-protected computers. The study app we will be using is HIPAA compliant and approved by Emory IT services. Personal identity will be protected in any publication.

Adequacy of Protection Against Risks

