Recruitment and Informed Consent: Aim 2 will require prospective recruitment of 70 (expect 30 screen fails for an enrollment of 40) subjects. Recruitment will be through Latino health centers. Permission to perform this study will be sought from the Emory University IRB. At the time of screening, the trained study staff will discuss the study with the subject and give them all the information listed above in language understandable at the level of the subject and all information needed to make an informed choice about participation. Informed consents will be obtained prior to initiating any study procedure.

Protection Against Risk: Risk will be minimized to the subjects by continuous monitoring and water breaks when needed. Risk to confidentiality will be reduced by using non-identifying participant numbers and removing all identifiers as early as feasible. Only study personnel will have access to identifying data. Coaches will be on a first name basis with subjects but not have access to non-relevant data.

Potential Benefits of the Proposed Research to the Participants and Others

The proposed research has substantial potential benefits for these men. The positive engagement of Hispanic men in a successful diabetes prevention program will allow for expansion into other communities as well as with children and adolescents and women, ultimately resulting in improved quality of life in the Hispanic community. Each man in the study will undergo assessments not typically clinically available.

Any new diagnosis of diabetes or potential hypertension that occurs during the research studies will be shared with the subject and they will be referred to their doctor or health clinic.

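### The plan secures no Garmin wear before the programme starts, so the only comparator for objectively measured activity (Aim 2b) may already contain soccer sessions

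*Combined protocol and SAP*

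**What the plan says.** Aim 2b reads "To explore preliminary signals for improvements in objectively-measured PA", followed by diet, fitness and body composition. The Background explains why activity matters here: "previous DPP translation trials typically lack reporting of PA results, one of the pillars of the program, specifically objectively-measured PA".

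On the device, Study Assessments asks participants to "wear a Garmin fitness tracker for the duration of the study to measure steps and moderate and vigorous activity". Under Protection of Human Subjects, the research material includes "physical activity assessments and tracking of physical activity via a fitness tracker throughout the study". Neither place gives an issue date, a run-in, a minimum wear time or a rule for the baseline value. The other wearable is fitted only in sessions and games. The activity assessments named in the research material are not described further.

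On timing, three places differ:
- Study Assessments: "Assessments will be conducted at baseline during the first soccer practice".
- Specific Aims: "After a baseline assessment visit, participants will attend soccer practice twice/week for 12-weeks".
- Recruitment: an information session at the field for "informed consent and confirmatory baseline assessments including BMI, blood pressure, HbA1c and exercise pre-participation risk screening".

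Recruitment and Informed Consent adds: "Informed consents will be obtained prior to initiating any study procedure". The Data Analytics and Statistical Plan promises standardized mean differences and effect sizes with 95% CIs, and does not define baseline for tracker data.

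**The concern.** With no control arm, the pre value is the only comparator. Most baseline measures, such as weight or blood pressure, can be taken in minutes just before the first practice. Habitual activity cannot, because it needs several days of wear. A tracker handed out at the first practice yields no pre-programme days at all, and the earliest wear available then falls in a week that contains the intervention.

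Consent must come before any study procedure, so clean wear can fall only between consent and the first practice. No section sets or uses that interval. If it is not used, the days cannot be recovered later. The planned confidence interval gives no warning, because it describes sampling variation around whatever change is computed, including a shifted one. The pilot is meant to inform later randomized trials, so a distorted activity signal would be carried forward.

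**Working it through.** The plan states no figure for activity change, so there is none to reproduce. The check applies arithmetic to the plan's own schedule.

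**Inputs from the documents**
- Conditioning phase: two one-hour sessions a week, 2 × 60 = 120 min/week (Study Assessments).
- Soccer before entry: 0 min/week, because men already playing are ineligible (Inclusion criteria).
- League phase: one game a week, length not stated (Specific Aims).
- Part of each session goes to curriculum discussion (Aim 1a). Baseline testing takes place in the first practice (Study Assessments). Both make 60 counted minutes a ceiling.

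**Assumed, not in the documents**
- Active minutes per session *m*: 30 to 60.
- Attendance *a*: 80% to 100%.
- Sessions falling in the baseline window *k*: 0, 1 or 2.
- Game length: 45 to 90 min.

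**Step 1: error in each later change.** Error = −(*k* × *m* × *a*), in min/week.

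| *k* | Ceiling (*m* = 60, *a* = 100%) | Low end (*m* = 30, *a* = 80%) |
|---|---|---|
| 0 (full week worn first) | 0 | 0 |
| 1 | −60 | 1 × 30 × 0.8 = −24 |
| 2 | −120 | 2 × 30 × 0.8 = −48 |

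**Step 2: what this does to the sessions' own part of the change, at the ceiling.**
- Week 12, window in the last conditioning week: 120 − 0 = +120 with a clean baseline; 120 − 60 = +60 with one session in it; 120 − 120 = 0 with two.
- Week 24, window containing one game: +45 to +90 with a clean baseline. With two sessions in it, 45 − 120 = −75 to 90 − 120 = −30, an apparent decline.
- One year, assuming no soccer by then: 0 with a clean baseline, −120 with two sessions in it.

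**Step 3: what remains if session time is removed at analysis.** The remaining error is −(7 × *d*), where *d* is the week-1 shift in other activity in min/day. The documents give no value for *d*. For an illustrative *d* of −10 to +10, the error runs from +70 to −70 min/week, so its direction is unknown.

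**Step 4: follow-up windows.** The week-12 assessment follows the conditioning phase, and league play begins at the same mark. A week taken around that visit could hold two practices, one game or neither. Without a stated window, the follow-up value is also left open.

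**The case against.** The strongest reply is that the harm needs two facts the plan does not state: hand-out at the first practice, and use of first-week wear as the pre value. Specific Aims puts a baseline visit ahead of the practices. The list of checks at the consent session is introduced as non-exhaustive, and wear for the whole study could run from consent. That stands. A reader might infer that the baseline will be contaminated, but the documents support only that nothing prevents it.

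Second, the session part is largely recoverable. Sessions are scheduled, recorded with a separate device, and absent before entry by eligibility. That also stands. What cannot be recovered is the unworn pre-programme time.

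Third, a reader might infer that the bias always runs against the programme. That is certain only for uncorrected session minutes. After correction the sign is open.

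Fourth, a reader might add a separate loss from the 48 hours of rest required before testing. If the tracker is issued at the first practice, those days precede wear and cannot lie in the baseline window, so the two effects do not simply add. The loss also depends on whether the rest days displace a session, so no single percentage is supportable. It is enough to keep those days out of every window.

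Finally, Aim 2b is exploratory in a 40-man feasibility pilot. That limits the weight of the point, but the remedy is small and available only before the first practice.

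**Conclusion.** The point holds as a gap in the plan. Study Assessments dates baseline at the first practice, no section places tracker wear before it, and the Garmin is the only device described for activity outside sessions and games. If first-week wear becomes the pre value, each later change in activity minutes is understated by up to 60 min/week (one session in the window) or 120 (two). Under the assumed session and attendance ranges this is 24 to 60 or 48 to 120. The error is 0 if a full week is worn first. The upper figures assume full attendance and every session minute counted as activity. They concern minutes; steps are not quantified.

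Only the exploratory activity signal is affected. A reader might infer that the pilot's main conclusion is at risk. It is not, because the central hypothesis concerns feasibility of implementation. The point should be fixed, with medium confidence, since the actual hand-out date is not known from the documents.

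**What to change.** 1. Reconcile Specific Aims, Recruitment and Study Assessments on when baseline is taken.
2. Issue the Garmin at the existing consent session once eligibility is confirmed.
3. Define baseline activity as a fixed window, for example 7 days with a stated minimum number of valid days, that ends before the 48-hour abstention period and the first practice. Name it as the pre value in the Data Analytics and Statistical Plan.
4. Use windows of the same length at weeks 12, 24 and 1 year. Leave out abstention and test days there too, and say whether each window falls inside or after a programme phase.
5. Keep men without pre-start wear out of the main activity change. Show them only in a sensitivity analysis that uses first-week activity with session time removed, and report their number.

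**Cost.** No new type of device is needed, since each participant already receives a Garmin. The lag between consent and the first practice is about 7 days, or 7 + 2 = 9 if baseline testing stays at the first practice. A few trackers will go to men who do not start. Waiting for confirmed eligibility avoids issuing up to 70 devices instead of about 40, given the 30 screen failures expected. Wearing the tracker may itself change activity in the baseline week; the documents give no size for this, and it should be stated as a limitation.

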Data and statistics will be managed by the PI and the study team using RedCap. Any paper forms will be kept in a locked cabinet in a locked office. Demographics and characteristics of the overall cohort will be tabulated using means and standard deviations or counts and percentages, as appropriate. Prior to analysis, continuous measures will be tested for normality. Non-normally distributed variables will be transformed prior to analysis or non-parametric approaches will be utilized. Linear regression will be used to control for anthropometrics and other factors that may influence improvement and will contain no more than five predictors at a time, given our sample size of 40. Standardized mean differences and effect sizes with associated 95% CI will be calculated for outcomes of interest.

Training of study team:

As stated above all staff and soccer coaches will receive adequate training of all study procedures. All study staff and collaborators will take CITI training upon hire.

Confidentiality: Screens will be used on the soccer fields for consent and study measurements. All participants will receive a study ID and this will be used on all paper and electronic forms. We will destroy all identifiers and any audio from key interviews after the study is complete.

References

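### No repeated-measures method is named for outcomes taken at four visits; one linear mixed model would reduce possible dropout bias in the exploratory 24-week and 1-year changes

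*Combined protocol and SAP*

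**What the plan says.** The statistical plan is one paragraph (Data Analytics and Statistical Plan). For effects it states: "Standardized mean differences and effect sizes with associated 95% CI will be calculated for outcomes of interest". The only model it names is a linear regression for factors that may influence improvement. For skewed outcomes: "Non-normally distributed variables will be transformed prior to analysis or non-parametric approaches will be utilized". It names no mixed model, GEE or repeated-measures ANOVA. It does not say which visits are contrasted, which men are analysed or how a missed visit is handled.

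The schedule is longitudinal. Study Assessments sets visits at baseline and after the 12-week conditioning phase, then: "Assessments will also be repeated at 24-weeks and 1 year from study initiation". Specific Aims adds: "We will also conduct a 1-year follow up assessment after 6 months of minimal contact". The outcomes at issue belong to Aim 2b: "To explore preliminary signals for improvements in objectively-measured PA, dietary behaviors, physical fitness and body composition outcomes".

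No allowance is made for men lost after enrolment. The recruitment target of 70 covers screening only ("expect 30 screen fails for an enrollment of 40", Recruitment and Informed Consent).

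**The concern.** A week-24 change computed from men with both a baseline and a week-24 value makes no use of the week-12 results of men who left in between. Those results carry information about what the week-24 values would have been. Week 12 is a plausible exit point: the programme then moves from two practices a week to one league game a week, which men are invited to join.

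If the men who leave are those who had improved least, the remaining men look better than the enrolled group. The mean change is then overstated, and so is any standardized difference built on it. There is no control arm in which similar loss might offset this. Specific Aims says the pilot is meant to inform later randomized trials, so an inflated Aim 2b effect size could be carried into their planning.

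**Working it through.** **Inputs from the documents.** Enrolment is 70 - 30 = 40, as stated. There is no power or precision figure to reproduce. The documents assume no retention rate for this trial. Background and Rationale cites 63-93% at 6 months for other, mostly female programmes; applied to 40 men this gives 0.63 x 40 = 25.2 and 0.93 x 40 = 37.2, so about 25 to 37 men at week 24. Losses of 7% and 37% are the two ends of that range and 22% is their midpoint.

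**Assumptions (not in the documents).** The 12- and 24-week changes are bivariate normal with SD 1 and correlation 0.5 or 0.7. The log-odds of loss rise by 1.0 per SD of worse change.

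**Formulas.**
- Completer estimate: mean 24-week change among men seen at week 24.
- Likelihood estimate, as from a mixed model with unstructured covariance: completer mean + slope x (mean 12-week change of all men seen at week 12 - mean 12-week change of completers), where the slope is that of 24-week on 12-week change among completers.
- When loss follows the 12-week change, completer bias = correlation x shift in the completers' mean 12-week change.

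**Results.** Overstatement of the 24-week mean change, in SD of change, for correlation 0.5 and then 0.7 (n = 40, 20,000 replicates per cell):

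| Assumed loss pattern | Loss | Completers | Mixed model |
|---|---|---|---|
| After week 12, follows 12-week change | 7% | 0.030, 0.046 | about 0 |
| Same | 22% | 0.096, 0.133 | about 0 |
| Same | 37% | 0.152, 0.216 | about 0 |
| Half before, half after week 12 | 37% | 0.166, 0.236 | 0.079, 0.113 |
| All before week 12 | 37% | 0.153, 0.218 | 0.153, 0.218 |
| Follows the unseen 24-week change | 37% | 0.309, 0.307 | 0.242, 0.168 |
| Random | 37% | 0 | 0 |

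Check of the third row: 0.152/0.5 = 0.304 and 0.216/0.7 = 0.309, so both imply a shift of about 0.31 SD at week 12, as the bias formula requires.

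**Coverage of the 95% CI.** In the first pattern, completers have 95-94% at 7% loss and 89-81% at 37%; the model has 95-96%. Under random loss at 37% the model gains only a little precision (RMSE 0.201 against 0.193 at correlation 0.5; 0.200 against 0.182 at 0.7).

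**Scale.** The CI half-width for a mean change in SD units is t(0.975, n-1)/sqrt(n): 2.028/6.083 = 0.333 at n = 37 and 2.064/5 = 0.413 at n = 25. The plan does not name the standardizer. If it is the baseline SD, with an assumed baseline/follow-up correlation of 0.7, the SD of change is sqrt(2 x 0.3) = 0.775 baseline SD, and 0.152-0.216 becomes 0.12-0.17.

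**Independent check.** A separate four-visit simulation with exchangeable correlation 0.6 or 0.8, 63% retention and loss after week 12 following the 12-week change gave 0.144 and 0.097 baseline SD for completers, against 0.00-0.01 for an unstructured likelihood model. The SD of change is sqrt(2 x 0.4) = 0.894 and sqrt(2 x 0.2) = 0.632, so these are 0.16 and 0.15 SD of change. That agrees with the table at correlation 0.5, which is the change correlation that exchangeability implies.

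**Simpler covariance.** A random-intercept model assumes one common correlation between visits. With baseline/follow-up correlation 0.7, the change correlation is (r - 0.4)/0.6, where r is the correlation between weeks 12 and 24. A change correlation of 0.5 needs r = 0.7, so the model is correct and its bias is about 0. A change correlation of 0.7 needs r = 0.82, so the model is misspecified; it leaves about 0.04 SD at 22% loss and 0.06 SD at 37%.

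**The case against.** The strongest reply is that the plan is silent, not wrong. A reader might infer that it prescribes a completer analysis; it does not, and it excludes no method. A reader might also infer that men who leave after week 12 lose all their data. On a visit-by-visit reading they still count in the 12-week change, and only the later estimates are affected. Both points stand and limit the claim.

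Next, the size depends on an assumed mechanism. Background and Rationale lists motivation, time and resources as barriers to activity, not poor response. It also cites adherence above 90% in recreational soccer interventions. Adherence is not visit retention, but together with the text messages and the tracker kept on completion it makes loss near 7% plausible. The overstatement is then 0.03-0.05 SD against a half-width of 0.33. Even the 0.22 SD at 37% loss is about half of 0.41. Moreover, the one 63% figure tied to a described programme is completion of 13 weeks, which is close to the loss-before-week-12 pattern, where the model gives no gain here. All of this stands as a limit on size. It does not favour the completer estimate, which was no less biased than the unstructured model in any pattern examined.

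Finally, the remedy is partial. Outcomes on the non-parametric route are not helped. Men are to "wear a Garmin fitness tracker for the duration of the study", so activity has no visit value until one is defined, and objectively measured activity heads the Aim 2b list. This stands too.

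A reader might further infer that the regression is faulty because it "will contain no more than five predictors at a time, given our sample size of 40" although fewer men may have the outcome. That wording is a ceiling, so fewer predictors are already allowed, and coefficient tests stay valid with fewer men.

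**Conclusion.** The point holds as a low-cost improvement to an under-specified analysis. With outcomes at four visits and no repeated-measures method named, the 24-week and 1-year changes are open to dropout bias that data already collected could reduce. Under loss after week 12 that follows the 12-week response, the 24-week overstatement runs from 0.03-0.05 SD of change at 7% loss to 0.15-0.22 SD at 37%. This rests on assumed retention, strength of selection and correlation, and on the inference that each later change uses only men seen at that visit. The 1-year change is exposed in the same way, but its size was not calculated.

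The effect is negligible with high retention and absent with random loss. The documents do not support two stronger readings. One is that the feasibility conclusion is at risk: it is the central hypothesis and does not rest on these estimates. The other is that a mixed model would remove dropout bias in general: it gives no gain in the calculation for loss before week 12, removes only part when loss depends on unseen values, and cannot replace a control arm.

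**What to change.** Add to Data Analytics and Statistical Plan:

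- For each continuous outcome measured at the four visits, after any planned transformation, estimate mean change from baseline with 95% CI at each visit from one linear mixed model. Use visit as a categorical effect, all enrolled men with any data, unstructured covariance and small-sample degrees of freedom.
- Derive the standardized mean differences from these estimates and name the standardizer.
- Give completer results as a sensitivity analysis and report the number lost before each visit.
- If the unstructured model does not converge and a random intercept is used instead, state that it reduces the bias but may not remove it.
- State that the model does not correct loss before week 12 and only partly corrects loss that depends on unseen values.
- Keep outcomes on the non-parametric route there, labelled as completer results. Include Garmin activity only if visit values are defined beforehand.

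The planned regression for predictors of improvement can stay as it is. The cost is a few sentences and slightly more analysis work in standard software, with no extra data or visits. The price in assumptions is reliance on loss depending on observed data.
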